- 5. Participant has an intact protective cutaneous sensation as measured with the lpswich test for loss of protective sensation (10-gram monofilament);
- 6. Participant has an intact cutaneous barrier, with or without the presence of hyperkeratotic lesions, with or without concomitant tinea pedis or

CONFIDENTIAL

interdigital maceration, or with or without a history of previous skin ulceration, but without active or current pedal ulceration;

- 7. Participant must be a satisfactory candidate for the proposed topical antifungal or placebo intervention;
- 8. Participant must display the ability to understand and give informed consent to participation, on a voluntary basis, in the research study.

Exclusion criteria for this study are:

- 1. Presence of dermatophytoma, defined as thick masses of fungal hyphae and necrotic keratin between the nail plate and nail bed;
- 2. Use of any systemic antifungal therapeutic agents within 7-months before the baseline visit, or topical antifungal agent on the feet within 1 month preceding the baseline measurement visit;
- 3. Candidate with moccasin tinea pedis involving greater than 50% of either plantar surface;
- 4. Candidate requires the use of narcotic analgesic or non-steroidal antiinflammatory drug/s for 48 hours prior to baseline visit or at any follow-up clinical evaluations;
- 5. Candidate has an active drug/alcohol dependence or abuse history;
- 6. Candidate has a loss of protective pedal sensation or open cutaneous compromise involving the ipsilateral foot;
- 7. Candidate has trauma to the nail that resulting in permanent nail plate discoloration or shape;
- 8. Candidate displays radiographic evidence of abnormal lytic or proliferative bone lesion in the toe/s of interest, including recent or healing of an acute fracture, if clinical inspection indicates the potential presence of subungual exostosis (radiographs will be obtained and paid for in the course of usual and customary care, outside of participation in this study);
- 9. Candidate has had previous nail matrix ablative surgery, either chemical or cold steel, on any of the involved digits;
- 10. Candidate presents systemic or local contraindications to the proposed application of the topical antifungal nail solution or the placebo agent, such as an uncontrolled cardiac, neurological, hepatic, renal, metabolic, or hematological disease or impairment that has been identified;

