An *adverse event* (AE) is any symptom, sign, illness or experience that develops or worsens in severity during the study. Intercurrent illnesses or injuries will be regarded as adverse events. Abnormal results of diagnostic procedures are adverse events if the abnormality:

- results in study withdrawal;
- is associated with a serious adverse event;
- is associated with clinical signs or symptoms;
- leads to additional treatment or to further diagnostic tests; and
- is considered by the investigators to be of clinical significance.

Serious Adverse Event

Adverse events are classified as serious or non-serious. A *serious adverse event* is any AE that is:

- fatal;
- life-threatening;
- requires or prolongs hospital stay;
- results in persistent or significant disability or incapacity;
- a congenital anomaly or birth defect; and
- an important medical event.

Important medical events are those that may not be immediately life threatening but are clearly of major clinical significance. They may jeopardize the participant and may require intervention to prevent one of the other serious outcomes noted above. For example, drug overdose or abuse, a seizure that did not result in in-patient hospitalization, or intensive treatment of bronchospasm in an emergency department would typically be considered serious.

CONFIDENTIAL

All adverse events that do not meet any of the criteria for serious will be regarded as *non-serious adverse events*.

Adverse Event Reporting Period

The study period during which adverse events must be reported is normally defined as the period from the initiation of any study procedures to the end of the study treatment follow-up. For this study, the study treatment follow-up is defined as 30 days following the last administration of study treatment.

Preexisting Condition

A preexisting condition is one that is present at the start of the study. A preexisting condition should be recorded as an adverse event if the frequency, intensity, or the character of the condition worsens during the study period.

General Physical Examination Findings

At screening, any clinically significant abnormality should be recorded as a preexisting condition. At the end of the study, any new clinically significant findings/abnormalities that meet the definition of an adverse event must also be recorded and documented as an adverse event.

Post-study Adverse Event

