All unresolved adverse events should be followed by the investigator until the events are resolved, the participant is lost to follow-up, or the adverse event is otherwise explained. At the last scheduled visit, the investigator should instruct each participant to report any subsequent event(s) that the participant, or the participant's personal physician, believes might reasonably be related to participation in this study. The investigator should notify the study sponsor of any death or adverse event occurring at any time after a participant has discontinued or terminated study participation that may reasonably be related to this study. The sponsor should also be notified if the investigator should become aware of the development of cancer or of a congenital anomaly in a subsequently conceived offspring of a participant that has participated in this study.

Abnormal Laboratory Values

A clinical laboratory abnormality should be documented as an adverse event if any one of the following conditions is met:

- The laboratory abnormality is not otherwise refuted by a repeat test to confirm the abnormality;
- The abnormality suggests a disease and/or organ toxicity; and
- The abnormality is of a degree that requires active management; e.g. change of dose, discontinuation of a drug, more frequent follow-up assessments, further diagnostic investigation, and the like.

Hospitalization, Prolonged Hospitalization or Surgery

CONFIDENTIAL

Any adverse event that results in hospitalization or prolonged hospitalization should be documented and reported as a serious adverse event unless specifically instructed otherwise in this protocol. Any condition responsible for surgery should be documented as an adverse event if the condition meets the criteria for an adverse event.

Neither the condition, hospitalization, prolonged hospitalization, nor surgery are reported as an adverse event in the following circumstances:

- Hospitalization or prolonged hospitalization for diagnostic or elective surgical procedures for a preexisting condition. Surgery should *not* be reported as an outcome of an adverse event if the purpose of the surgery was elective or diagnostic and the outcome was uneventful.
- Hospitalization or prolonged hospitalization required to allow efficacy measurement for the study.

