- Hospitalization or prolonged hospitalization for therapy of the target disease of the study, unless it is a worsening or increase in frequency of hospital admissions as judged by the clinical investigator.

Recording of Adverse Events

At each contact with the participant, the investigator must seek information on adverse events by specific questioning and, as appropriate, by examination. Information on all adverse events should be recorded immediately in the appropriate adverse event module of the source document and case report form (CRF) (Attachments 4-7), and in the adverse event-serious adverse event form (Attachment 8). All clearly related signs, symptoms, and abnormal diagnostic procedure results should be recorded in the source document and grouped under one diagnosis.

All adverse events occurring during the study period must be recorded. The clinical course of each event should be followed until resolution, stabilization, or until it has been determined that the study treatment or participation is not the cause. Serious adverse events that are still ongoing at the end of the study period must be followed to determine the outcome. Any serious adverse event that occurs after the study period and is considered to be possibly related to the study treatment or study participation should be recorded and reported.

Reporting of Serious Adverse Events

• Study Sponsor Notification by Investigator

A serious adverse event must be reported to the study sponsor by telephone within 24 hours of the event. The Adverse Event/Serious Adverse Event (AE/SAE) form, Attachment 8, form must be completed by the investigator and faxed to the study sponsor within 24 hours. The investigator will keep a

CONFIDENTIAL

copy of this SAE form on file at the study site. Serious adverse events will be reported by phone to the pharmacovigilance services of Marlinz Pharma, at:

[name] Marlinz Pharma [name] [contact]

At the time of the initial report, the following information should be provided:

- Study identifier
- Study clinic address
- Participant number
- A description of the event
- Date of onset
- Current status

- Whether study treatment was discontinued
- The reason why the event is classified as serious
- Investigator assessment of the association between the event and study treatment

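### The adverse event rules conflict when a preexisting condition worsens on study and leads to a hospital admission for an elective operation or diagnostic procedure

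*Protocol*

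**What the plan says.** All the relevant text is in the protocol, under Safety and Adverse Events.

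- **Definitions, Adverse Event.** An AE is "any symptom, sign, illness or experience that develops or worsens in severity during the study".
- **Preexisting Condition.** "A preexisting condition should be recorded as an adverse event if the frequency, intensity, or the character of the condition worsens during the study period".
- **Hospitalization, Prolonged Hospitalization or Surgery, opening paragraph.** An AE that leads to a hospital stay is an SAE unless the protocol specifically says otherwise. It continues: "Any condition responsible for surgery should be documented as an adverse event if the condition meets the criteria for an adverse event".
- **Same section, lead-in to the exemptions.** "Neither the condition, hospitalization, prolonged hospitalization, nor surgery are reported as an adverse event in the following circumstances".
- **First exemption bullet.** "Hospitalization or prolonged hospitalization for diagnostic or elective surgical procedures for a preexisting condition". A second sentence in this bullet says that elective or diagnostic surgery with an uneventful course is not to be reported as the outcome of an AE.
- **Third exemption bullet (treatment of the target disease).** The exemption applies "unless it is a worsening or increase in frequency of hospital admissions as judged by the clinical investigator".
- **Recording of Adverse Events.** Every AE in the study period has to be recorded.

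**The concern.** The lead-in exempts the condition itself, not just the hospital stay or the operation. The first bullet then defines the exempt circumstance by the kind of procedure and by the condition being preexisting. It does not ask whether the condition stayed stable. Whether an admission is elective describes how it was scheduled. It does not show that the underlying condition was unchanged.

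A worsened preexisting condition can therefore meet the AE criteria and fall inside the exemption at once. What is at stake is consistent safety classification across the nine sites listed in the protocol (A to H, and J). An event that one site treats as an SAE could be left out entirely at another.

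**Working it through.** No figure in the protocol bears on this point, so the check is a comparison of the rules on test cases.

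**Case 1. A preexisting condition worsens on study, and the participant is admitted for an elective operation or diagnostic procedure for it.**

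| Rule | Result |
|---|---|
| AE definition | AE, because something worsened during the study |
| Preexisting Condition | Record as an AE |
| Sentence on conditions responsible for surgery (if there is an operation) | Document as an AE, because the AE criteria are met |
| Hospitalization sentence | SAE, unless the protocol specifically instructs otherwise |
| First exemption bullet with its lead-in | Neither the condition nor the stay is reported as an AE |
| Recording of Adverse Events | Record, if it is an AE |

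The rows do not agree. The exemption also qualifies as a specific instruction otherwise, so it can switch off the SAE rule as well. Because the protocol defines an SAE as an AE meeting a seriousness criterion, an event not classed as an AE cannot become an SAE. It would then miss the 24-hour report to the sponsor, the written narrative due within the following 48 hours, the EC/IRB report within 10 working days, and the count of serious events under Medical Monitoring.

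**Case 2. The same worsened condition is treated electively without admission.** The first sentence of the bullet concerns hospital stays only, so it does not apply. The second sentence drops only the surgery as an outcome. The condition remains an AE. There is no conflict.

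**Case 3. A preexisting condition is unchanged, and the participant is admitted for an elective procedure.** The condition is not an AE under the Preexisting Condition rule, and the exemption agrees. There is no conflict.

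**Case 4. The onychomycosis itself worsens and leads to an elective admission.** It is both the target disease and a condition present at the start. The third bullet's exception keeps it reportable, while the first bullet, read alone, exempts it. Again the rules disagree.

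The conflict is thus confined to worsening combined with admission for an elective or diagnostic procedure (cases 1 and 4). The third bullet's exception is loosely worded, but it shows that the drafters wrote in worsening where they had it in mind. The first bullet has nothing equivalent.

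**The case against.** The strongest reply is that the first bullet is plainly meant for procedures on unchanged conditions, and that the surrounding text protects a real AE. The sentence just before the exemptions says to document the condition if it meets the AE criteria. The recording section covers all AEs and requires specific questioning at each contact. The Statistical Methods section separately collects local and systemic complications. The bullet's second sentence also presupposes that an AE can exist alongside elective surgery. This is a natural reading and probably the intended one, but the text does not state it, and the lead-in names the condition among the things not reported.

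Several stronger readings are tempting, and the documents do not support them.

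- **That every preexisting condition treated electively drops out.** The bullet covers hospital stays only; case 2 shows that the condition stays recordable without one.
- **That such events are removed from the safety data.** Three rules still point to recording, so the most that can be said is that an event may go unreported.
- **That earlier ulcers or diabetes make this a likely route for harm to vanish.** Entry is allowed "with or without a history of previous skin ulceration", but not with an active ulcer. A new ulcer would develop on study and be an AE in its own right. The exclusions for lost protective sensation, non-palpable pulses and HbA1c above 8% weaken the diabetes example.
- **That the number of lost events can be estimated.** The protocol gives no rate for worsening followed by elective admission, and any figure would only restate an assumption.

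**Conclusion.** The point holds in its narrow form. For a preexisting condition that worsens on study and leads to a hospital admission for an elective operation or diagnostic procedure, the protocol says both that it is an AE (and an SAE because of the admission) and that it is not reported. Sites could resolve this differently, and an SAE may go unreported.

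The severity is minor. The frequency cannot be derived from the protocol. The judgement that such admissions are probably rare rests on the setting: outpatient podiatry offices, a topical over-the-counter product, and few expected AEs. The primary endpoint, randomization and sample size are not affected.

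**What to change.** Reconcile the sections by adding one sentence to the first exemption bullet. It should say that the exemption does not apply when the preexisting condition has worsened during the study period, judged by the criteria already given under Preexisting Condition. In that case the condition is recorded as an AE, and the resulting hospitalization is handled under the existing SAE rule. This follows the approach of the third bullet and leaves the exemption intact for unchanged conditions. The protocol's own rule turns on worsening, so a further restriction to procedures planned before enrolment is not needed to remove the conflict.

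The cost is one sentence of protocol wording and possibly an occasional extra AE or SAE report. No visits, staff or participants are added.
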